Written informed consent for participation in the study must be obtained from subjects before initiation of any study-related activities. Following informed consent, subjects will be assigned a unique subject identification number and will be considered to be enrolled in the study. Eligibility for advancing to the next stage of the study will be evaluated by the Investigator based on the defined inclusion and exclusion criteria. Subjects will be assessed for pain intensity and disability.

B.6.3. Entry Criteria Evaluation

The eligibility of subjects who have consented participation will be assessed based on the inclusion and exclusion criteria. Study subjects must meet all of the study inclusion criteria and none of the study exclusion criteria to be eligible. Assessments for eligibility include average pain intensity (which will be used as Baseline pain intensity), medication usage, medical records and history, and the Investigator's clinical judgment. Subjects with confirmed eligibility will proceed to Baseline assessment, while subjects who do not will be discontinued from the study.

B.6.4. Baseline

Before a subject is randomized, a subject will be requested to fill out standard questionnaires that will assess extent of disability, use of medications, and quality of life. The medical and surgical history of the subject will be collected. At this visit and subsequent visits, the subject will be assessed for adverse events, medication usage and be reminded to not increase pain medications from baseline through the 3-Month Visit.

Pre-operative assessments will follow the standard of care for SCS therapy and be determined by the site Investigator.

B.6.5. Randomization

Subsequent to completing Baseline assessments, qualifying subjects will be randomly assigned to either one of the two study treatment groups: DTM-SCS programming or Conventional SCS programming (active comparator). Randomization will be stratified by gender and whether the subject has leg pain or no leg pain at Baseline. Randomization will be done at each study site by randomly permuted blocks.

B.6.6. SCS Trial Phase

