Analysis of both secondary endpoints will be based on a repeated measures approach that accounts for within subject correlation. Treatment group status for the repeated measures models will be based on treatment status at the current time point (i.e. it will be based on treatment status incorporating potential crossover, not necessarily the original randomized assignment).

B.7.5. Additional Data Collection

These following data will be collected:

- Frequency of treatment emergent adverse events
- Comparison of opioid medication usage from baseline at 3, 6, 9 and 12 months after device activation between the two arms
- Comparison of mean change from Baseline in Leg Pain VAS, evaluated at 3, 6, 9 and 12 months after device activation for subjects with baseline leg pain VAS score ≥ 5 between test and control
- Comparison of Leg Pain Treatment Success, measured as at least a 50% reduction in Leg Pain VAS, evaluated at 3, 6, 9, and 12 months after device activation for subjects with baseline leg pain VAS score ≥ 5 between test and control
- Comparison of patient satisfaction between two arms
- Patient Global Impression of Change, evaluated at 3, 6, 9 and 12 months after device activation
- Comparison of Patient Global Impression of Change between two arms

- Comparison of ODI change from baseline at 3, 6, 9 and 12 months after device activation between the two arms
- Comparison of quality of life (QoL) change (from EuroQol EQ-5D-5L) from baseline at 3, 6, 9 and 12 months after device activation between the two arms
- Quality of paresthesia at 3, 6, 9 and 12 months, comparison between test and control
- Percentage of subjects that crossover
- Comparison of mean change from last visit prior to crossover to 12 months visit. This analysis censors data post-crossover.
- Activity level based on Intellis™ adaptive data log (when available)
- Analysis of additional evaluable data items will be based on treatment status at the current time point (i.e. it will be based on treatment status incorporating potential crossover, not necessarily the original randomized assignment).

B.8. Evaluation Criteria

B.8.1. Effectiveness

Results of the tests and standard questionnaires will be recorded in Case Report Forms at Baseline and during follow-up visits. Changes from Baseline will be calculated and compared between the two groups.

Effectiveness will be measured for each subject using the following tests:

- Pain

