 - Visual Analog Scale (VAS, 10 cm) at Baseline, End of Trial Phase, Months 1, 3, 6, 9 and 12
- Disability
 - Oswestry Disability Index Questionnaire
- Quality of Life
 - EuroQol EQ-5D-5L
- Impression of Change in Quality of Life
 - Patient Global Impression of Change
- Satisfaction with Therapy
 - Subject Satisfaction Questionnaire

Study personnel will be appropriately trained for administration of each test.

B.8.2. Definition of Success

The subject's self-reported pain intensity score based on the 10 cm Visual Analog Scale (VAS) is considered the outcome measure for the efficacy component of the primary endpoint. VAS is a widely used outcome measure in assessing pain. It is a reliable and valid

method, which is easy to administer, and requires minimal training for the test administrator. VAS scores will be collected for both back and leg pain.

Study success will be declared if the non-inferiority test for the primary effectiveness endpoint is statistically significant.

There are no additional pre-specified subject or study-level success criteria for secondary and tertiary endpoints.

B.8.3. Safety

Safety will be assessed by characterizing adverse events at all study visits with descriptive statistics.

B.8.3.1 Definitions

An adverse event (AE) is any untoward medical occurrence in a subject associated with the use of the therapy under the study whether or not related to Intellis™ SCS system or the study procedures. An AE is also any event related to any underlying medical condition, present at baseline, which increases in severity or frequency by a clinically meaningful amount during the study as determined by the Investigator.

For all adverse events, the Investigator will provide an assessment of the relationship to the study. If the adverse event is study-related, the following parameters will be assessed: its seriousness, severity, treatment/intervention provided, and resolution.

As the efficacy measures in this study are back and leg pain, back and leg pain do *not* need to be reported as an adverse event unless it meets the definition of a serious adverse event. Investigators may, however, report any other pain-related adverse events during the study.

Pre-existing conditions will not be reported as an adverse event unless there has been a substantial increase in the severity or frequency of the problem, which has not been attributed to its natural history.

A serious adverse event (SAE) is an adverse event that

- Leads to death

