The following secondary endpoints do not have an associated hypothesis, and no significance level will be assigned to statistical tests that may be performed. Analysis of these endpoints will be based on a repeated measures approach that accounts for within subject correlation. Treatment group status for the repeated measures models will be based on treatment status at the current time point (i.e. it will be based on treatment status incorporating potential crossover, not necessarily the original randomized assignment).

- Comparison of Back Pain Treatment Success (responder rate), measured as subjects with at least a 50% reduction in Back Pain VAS, between test and control
- Comparison of mean change from Baseline in Back Pain VAS, between test and control

B.9.2.3 Additional Data

- Comparison of Leg Pain Treatment Success (responder rate), measured as subjects with at least a 50% reduction in Leg Pain VAS, between test and control for subjects with baseline leg pain VAS score ≥ 5
- Comparison of mean change from Baseline in Leg Pain VAS, between test and control for subjects with baseline leg pain VAS score ≥ 5
- *Satisfaction with Therapy*: Subject Satisfaction will be compared between test and control
- *Patient Global Impression Change*: The Patient Global Impression of Change from Baseline to follow-ups at 3-, 6-, 9- and 12-month visits after device activation will be compared between the treatment groups.

- *Oswestry Disability Index (ODI)*: The changes in ODI from Baseline to 3-, 6-, 9- and 12-months will be summarized as continuous variables and compared between the treatment groups.
- *Quality of Life*: The changes in the EQ-5D-5L instrument from Baseline to follow-ups at 3-, 6-, 9- and 12-months will be summarized as continuous variables and compared between the treatment groups.
- *Paresthesia Questionnaire*: Questions about the paresthesia will be used at 3-, 6-, 9-and 12-month visits and compared between test and control

B.9.2.4 Handling of Missing Data

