Missing data will be minimized by rigorous follow-up and investigator and site training. Additionally, for subjects who do not have a successful Trial Phase, results from the Trial Phase will be utilized for the primary endpoint as described in Section B.7.2. Effectiveness Assessment Definitions. Any other data will be imputed via Multiple Imputation. Additionally, sensitivity analyses for missing data will be performed. Unless otherwise specified, all other analyses will be based on the evaluable data with no imputation.

Details on imputation will be provided in a separate statistical analysis plan.

C. Risk Analysis

C.1. Description and Analysis of All Increased Risks to Subjects

Spinal Cord Stimulation (SCS) Risks:

DTM-SCS programming approach will be used with commercially available, FDA approved Intellis™ SCS system within approved indications for use. Anticipated potential adverse events resulting from the study are expected to be in line with adverse events already documented for SCS using a Standard programming approach.

There are known risks associated with the use of any SCS system. Known risks are associated with the implant procedure, the stimulation, the implanted device (not associated with stimulation) and external devices such as the charger and remote control. These are typical of commercial SCS systems. Subjects will be informed of these anticipated risks in the study consent process.

Risks of Surgery

Implanting a neurostimulation system has risks similar to spinal procedures, including spinal fluid leak (spinal fluid collection under the skin), headaches, swelling, bruising, bleeding, infection, or paralysis.

Subjects on anticoagulation therapy may be at higher risk for problems after surgery such as hematomas that could result in paralysis.

Spinal Cord Stimulation Risks

The implantation of a spinal cord stimulation system involves risks that are similar to other spinal procedures. In addition to those normally associated with surgery, implantation or use of a neurostimulation system includes, but is not limited to the following risks:

- Allergic or immune system response to the implanted materials
- Infection
- Lead or neurostimulator erosion through the skin or migration
- Leakage of cerebrospinal fluid
- Loss of pain relief may return patients to their underlying pain condition
- Persistent pain at the neurostimulator site

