As part of the study, subjects may be required to have fluoroscopic or X-ray images taken of their thoracic spine in addition to the imaging conducted to implant the leads. This may be beyond what is standard of care. The risk associated with these additional images has been considered and determined to be minimal since the total radiation dose will be approximately the same as one CT scan of the abdomen.

Study Risk Control Measures

The following will be done to mitigate risks associated with the implanted system:

- Investigators who are experienced with spinal cord stimulation implantation techniques will be utilized
- Instructions will be given to the study participants to ensure they can properly use the patient programmer and recharger system
- Subjects can turn off stimulation at any time during the study with the patient programmer or recharger
- Periodic monitoring of the study participants
- Written materials that contain precautions, warnings, and contraindications, as well as instructions on the use of the devices will be available and/or provided to the clinicians and subjects

Since the efficacy measure in this study is intensity of pain in the back and legs, pain in these areas does not need to be reported as an adverse event unless it meets the definition of a serious adverse event. However, Investigators may, at their discretion, report any other pain-related adverse events during the study.

C2. Minimization of Risks

Neurostimulation therapies, such as SCS, are used as an aid in the management of chronic, intractable pain that cannot be effectively managed with medications and/or other conservative treatments alone. Patients considered for neurostimulation therapy have typically had pain of long duration and have failed multiple therapeutic paths.

Medtronic has carefully designed and tested the Intellis AdaptiveStim Neurostimulation Systems to ensure the safety and performance for the treatment of chronic, intractable pain. Medtronic has completed an extensive risk analysis to ensure the identification of potential hazards and subsequent mitigation of these hazards to eliminate them entirely or reduce them to an acceptable level.

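### Non-serious new or worsening leg pain in subjects with baseline leg VAS below 5 is exempt from required AE reporting and outside both named leg-pain comparisons, and the safety sections conflict on which pain events must be captured

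*Combined protocol and SAP*

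**What the plan says.** **Reporting of pain as an adverse event.** C.1 (Study Risk Control Measures) gives the rule for back and leg pain: "pain in these areas does not need to be reported as an adverse event unless it meets the definition of a serious adverse event". B.8.3.1 states the same rule, again because back and leg pain are the efficacy measures. Neither place makes an exception for new onset or for worsening. Other pain is left open. B.8.3.1 says "Investigators may, however, report any other pain-related adverse events during the study", and C.1 says "Investigators may, at their discretion, report any other pain-related adverse events during the study".

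**Leg-pain analyses.** B.7.5 lists a mean-change comparison and a 50%-reduction comparison at 3, 6, 9 and 12 months, each "for subjects with baseline leg pain VAS score ≥ 5 between test and control". B.9.2.3 repeats the restriction for both: the responder rate, and "Comparison of mean change from Baseline in Leg Pain VAS, between test and control for subjects with baseline leg pain VAS score" of 5 or more. Under B.6.5, randomization is stratified by gender and by "whether the subject has leg pain or no leg pain at Baseline", so subjects without leg pain are a planned part of the trial.

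**Other relevant rules.** B.8.3.1 counts a clinically meaningful worsening of a condition present at baseline as an AE. B.8.3.2 has every AE assessed and recorded on a source worksheet from enrollment to study completion, but keeps events the investigator judges unrelated out of the EDC. It also points to the C.1 risk list, which includes "Persistent pain at the neurostimulator site". Under B.8.2, VAS is collected for back and leg with no baseline threshold.

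**The concern.** Exempting an efficacy measure from AE reporting is reasonable if the efficacy analyses pick up what AE reporting leaves out. For back pain they largely do: every subject enters with a back VAS of at least 6 and back pain is analysed in everyone. For leg pain they do not, because the named comparisons stop at baseline 5. For a subject with little or no leg pain at entry, leg pain that starts after lead placement is a new event, not the condition under treatment.

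B.2 makes characterizing the safety of DTM-SCS part of the study, B.7.5 lists the frequency of treatment-emergent AEs as an outcome, and B.1 argues that DTM-SCS may cause less uncomfortable stimulation. The AE table will therefore be read for a between-arm comparison. B.5.4 says subjects, implanting physicians and site staff are not blinded, and B.8.3.2 says there is no Data Monitoring Committee. If sites can choose whether to report a pain event, a difference between arms, or its absence, may partly reflect reporting habits.

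**Working it through.** The plan gives no figure on this point to reproduce. The check is a cross-reading, followed by a range for the number of subjects concerned.

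**Step 1. What covers new or worse leg pain?**

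| Situation | AE report required? | In a named leg-pain comparison? |
|---|---|---|
| Serious, any baseline | Yes (B.8.3.1, C.1; E.3 sets 48 hours for study-related SAEs) | Only if baseline leg VAS is 5 or more |
| Non-serious, baseline 5 or more | No | Yes, from Month 3 |
| Non-serious, baseline below 5 | No | No |
| Non-serious, after a failed Trial Phase, following lead explant | No | No further VAS is scheduled (Table 1) |

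The third row is the gap. It includes the stratum without leg pain and those whose leg VAS is above zero but below 5. The fourth row shows where VAS cannot stand in for AE reporting: B.6.7 follows these subjects for two weeks after explant specifically for adverse events. VAS is also taken at the end of the Trial Phase and at Month 1 (B.8.1), but the B.7.5 leg-pain comparisons begin at Month 3.

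**Step 2. Do the safety passages agree?**

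- B.8.3.1 treats clinically meaningful worsening of a baseline condition as an AE, then exempts non-serious back and leg pain without regard to worsening.
- B.8.3.2 has all AEs captured and refers to the C.1 list, which names pain at the neurostimulator site. B.8.3.1 and C.1 make pain other than back and leg pain optional.
- B.8.3.2 keeps events judged unrelated out of the EDC, so even a captured pain event reaches the analysis only if an unblinded investigator attributes it to the study.

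One site could record worsening leg pain under B.8.3.2 and another omit it under C.1, and each could cite the protocol.

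**Step 3. How many subjects?** Randomized N is about 135 (B.5.5). The share *s* with baseline leg VAS below 5 is not given; assume 20% to 60%.

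- Number outside the comparisons = *s* × 135: 0.20 × 135 = 27 and 0.60 × 135 = 81.
- If 5% of them (assumed) had new or worse leg pain, expected cases are 27 × 0.05 = 1.35 and 81 × 0.05 = 4.05.
- Chance of at least one such case = 1 − 0.95^n: 1 − 0.95^27 = 75% and 1 − 0.95^81 = 98%.

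The last two lines show only that such cases would not be remote. They do not estimate a rate.

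**The case against.** The defence has five parts.

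- **The exemption is permissive and has an exception.** It says such pain need not be reported, not that it must not be, and serious events stay reportable. This stands. A reader might infer that leg pain in this group cannot enter the AE data at all; the text does not say that.
- **The data exist.** Leg VAS is collected from everyone, B.8.1 promises between-group comparison of changes from Baseline on the listed tests, and B.9.2 promises descriptive summaries of outcome data. A reader might infer that new leg pain would vanish from the trial; it would not, because the scores are in the database. But the general sentences name neither leg pain nor worsening, the specific text restricts to 5 or more, and a mean change can hide individual worsening.
- **B.8.3.2 requires capture.** This weakens any claim that other pain events are reportable solely at the investigator's choice. One could also separate recording on a worksheet from reporting. The protocol does not draw that distinction, so the passages still need reconciling.
- **The cut-off is sensible for efficacy.** A 50% reduction is undefined at zero and unstable near it. This stands for the responder comparison. It gives no reason to leave out a worsening summary, since subjects starting near zero have room mainly to get worse.
- **Any bias is unquantified.** This stands. A reader might infer that AE frequency is under-counted, or under-counted more in one arm. The documents give no capture rates, so neither the size nor the direction of a difference can be stated.

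**Conclusion.** The point holds in this form. Non-serious new or worsening leg pain in subjects with baseline leg VAS below 5 is outside required AE reporting and outside both named leg-pain comparisons. No specified analysis targets new onset or worsening, although the scores are collected. Separately, B.8.3.1 and C.1 conflict with the AE definition in B.8.3.1 and the capture rule in B.8.3.2, which leaves room for unblinded sites to report pain events differently by arm.

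The affected group is 27 to 81 of about 135 subjects if 20% to 60% start below 5; that share is an assumption. The finding does not touch the primary endpoint, and it does not show that any harm would be missed or that either arm would be favoured. B.9.2.4 defers imputation details to a separate statistical analysis plan. If that plan already contains an all-subject leg-pain worsening table, the analysis half of this point falls and the reporting conflict remains.

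**What to change.** 1. **Add one table.** Prespecify, by arm, leg VAS change from Baseline, the number with new-onset leg pain, and the number worse than Baseline by a stated threshold. Include all randomized subjects with leg VAS data regardless of baseline score, alongside the existing subset at 5 or more. Use the end-of-trial and Month 1 scores as well as Months 3 to 12, and say whether visits after the Month 6 crossover option are shown by randomized or current treatment.
2. **Reconcile B.8.3.1, B.8.3.2 and C.1.** Limit the exemption to pre-existing back or leg pain that is not clinically worse than Baseline. Require capture of new-onset or worsened back or leg pain and of other pain-related AEs.
3. **Change the EDC filter for these events.** Enter them with the investigator's relatedness judgement as a recorded field, so that the judgement does not decide whether the event is in the database. Without this, step 2 would still leave out events judged unrelated.

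The table needs no new data. The wording changes bring somewhat more AE entries at sites and a higher reported AE count, which should be explained when results are set beside studies that used the narrower rule.

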All subjects enrolled in the study are expected to complete all scheduled visits through the follow up visit 12 months after Device Activation. A Study Completion eCRF should be completed at the end of this visit. If there is an ongoing study related adverse event, subjects will be followed until resolution of that adverse event or determination that the adverse event is not expected to change.

B.6.21. Study Suspension and Termination

Subjects will be considered to have completed all study requirements following the completion of the follow up visit 12 Months after Device Activation. Each clinical site will be considered to have completed study requirements at the end of the required monitored close out visit. The study will be considered closed when all of the requirements of this Investigational Plan have been fulfilled, all close out visits have been completed and all Sponsor and Investigator reports have been issued and reported to the IRB.

SGX, the Investigators, or the IRB(s) may suspend or terminate the study early at any time. If the study is suspended or terminated prematurely, all subjects that are still enrolled will be terminated from the study. A Study Completion eCRF will be completed noting that the study has been terminated. If there is an ongoing adverse event related to the device or treatment, the subject will be followed until resolution of the adverse event or determination that the adverse event is not likely to change.

Subsequent follow-up of the subjects after study completion will be the responsibility of the subject's personal physician.

SGX reserves the right to terminate the study but intends only to exercise this right for reasons related to the protection of subjects or valid scientific or business reasons. SGX will notify Investigators and IRBs in writing in the event of study termination.

SGX reserves the right to stop the enrollment of subjects at any clinical site at any time after the clinical site initiation. Possible reasons for suspending or terminating a clinical site may include, but are not limited to:

- Non-compliance by Investigator
- Failure to obtain proper written informed consent
- Repeated failure to complete or submit eCRFs in a timely manner
- Failure to report SAEs to the Sponsor within 48 hours of knowledge of the event and to reviewing IRB in accordance with its policies
- Repeated failure to comply with clearance of queries generated during monitoring of the study
- Inactivity

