- Leads to serious deterioration in the health of the subject, that either results in
 - a life-threatening illness or injury (life-threatening is defined as at risk of death at the time of the event), or
 - a permanent impairment of a body structure or a body function, or
 - in-patient hospitalization or prolongation of existing hospitalization (in-patient hospitalization is defined as a hospital admission for a period of greater than 24 hours), or
 - medical or surgical intervention to prevent life-threatening illness or injury or permanent impairment to a body structure or a body function,
- Leads to fetal distress, fetal death, or a congenital abnormality or birth defect

Those known adverse events related to the device, procedure or therapy are listed in the section C. (Risk Analysis) of this Investigational Plan.

B.8.3.2 Reporting

All AEs and SAEs will be assessed and captured from enrollment through the completion of the study on the Adverse Event Source Worksheet. AEs and SAEs will be reported as required by the IRB.

All Adverse Events (see list in section C.1.) assessed/determined to be study-related study will document seriousness, severity, treatment/intervention provided, relationship to the device/procedure, and resolution.

Adverse events that are determined to be not study related by the investigator will not be reported in the EDC.

As would be the common practice when using commercial medical devices, device - related AEs may be reported by the site (per their institutional policy) to the Customer Service or Technical Support of Medtronic as specified in the manufacturer's labeling/manuals.

This is a post market, open-label study so Data Monitoring Committee will not be used.

B.9. Data Collection and Analysis

B.9.1. Data Collection

Study data will be collected using a secure Electronic Data Capture system meeting the requirements of 21 CFR part 11. Each data field completed via the EDC system is expected to have a verifiable source document. The clinical site will enter the data from the source documents directly into the EDC system. Subject confidentiality will be maintained, and each subject will be identified only by the assigned study subject number. Subject names will not be published. Data collection is summarized in Table 1.

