The Investigator will also be responsible for filing an annual study progress report to the IRB as per IRB guidelines. The Investigator and/or Sponsor, as required by local regulations, are required to report in writing to the IRB, notice of completion, termination, or discontinuation of the study. If the study is discontinued for safety concerns, the Investigator and/or Sponsor will notify the IRB immediately.

The Investigator is also responsible for recording and assessing the relationship to the study and the seriousness of Adverse Events. Investigators must report any study related serious adverse event (SAE) to the sponsor within 48 hours of knowledge of the event and to the IRB as per their regulations.

The Investigator is also responsible for promptly reporting to the Sponsor any deviations and exceptions to this investigational plan and to the IRB per their requirements.

E.4. Informed Consent Materials

Informed consent must be obtained from all subjects prior to study participation. Informed consent will be obtained by the Investigator or an Investigator-designated healthcare professional as per GCP guidelines. An informed consent form (ICF) will be provided to potential subjects for their private evaluation. If a subject consents to participate, the ICF must be signed by the subject or a legally authorized representative of the subject. Study ICF must be approved by the IRB. Signed ICFs will be retained in the subject's study records at the clinical site. Subjects may be consented via a combination of mail and telephone calls. The RC will document the telephone calls and follow-up by signing the consent once the subject returns the signed consent. The RC will then provide a photo copy to the subject.

The ICF will be in compliance with the requirements set forth in 21 CFR 50, Protection of Human Subjects.

E.5 Investigators and Institutions

The clinical Investigators participating in this study will be chosen based on their qualifications and experience.

E.6. Amendments and Deviations

This investigational plan is to be followed by Investigators and all personnel involved in the clinical study. Any changes to the study covered by this investigational plan must be documented on a formal investigational plan amendment *prior to* implementation in the study.

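### The 48-hour SAE duty in E.3 is limited to study-related events while B.6.21 is not, so an SAE the investigator judges unrelated has no stated deadline for reaching the sponsor

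*Combined protocol and SAP*

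**What the plan says.** Two sections of the protocol attach a 48-hour limit to telling the sponsor about serious adverse events.

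- E.3 (Study Conduct) states the duty: "Investigators must report any study related serious adverse event (SAE) to the sponsor within 48 hours of knowledge of the event". The preceding sentence says who decides relatedness: "The Investigator is also responsible for recording and assessing the relationship to the study and the seriousness of Adverse Events".
- B.6.21 (Study Suspension and Termination) gives a list introduced by "Possible reasons for suspending or terminating a clinical site may include, but are not limited to". One item is "Failure to report SAEs to the Sponsor within 48 hours of knowledge of the event and to reviewing IRB in accordance with its policies".

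Two further sections decide what happens to an event judged unrelated.

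- B.8.3.1 (Definitions) asks for a relationship assessment for every adverse event. It then lists seriousness, severity, treatment and resolution as items to be assessed where the event is study-related.
- B.8.3.2 (Reporting) says "All AEs and SAEs will be assessed and captured from enrollment through the completion of the study on the Adverse Event Source Worksheet", with onward reporting to the IRB as the IRB requires. It also says "Adverse events that are determined to be not study related by the investigator will not be reported in the EDC", and makes no exception for serious events. The section ends by stating that a "Data Monitoring Committee will not be used".

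**The concern.** The same 48-hour limit is given two scopes. Under E.3 the investigator's causality opinion decides whether the sponsor is told promptly, and the sponsor does not see the event before that opinion is formed. B.5.4 says that site personnel cannot be blinded to the assignment, so the person forming it knows which programming approach the subject received.

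The documents do not define what counts as study-related. Both arms use a commercially available device within its labeling (A.2), so sites may differ on whether a complication of an ordinary trial or implant procedure qualifies. B.1 gives an example of the difficulty. The one serious event in the earlier feasibility study, an epidural abscess, is described as a recognised risk of an SCS trial, yet as unrelated to either programming approach. One site might call such an event study-related and another might not.

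At stake is the speed with which the sponsor can see serious events across up to 20 sites. The point concerns prompt notification, not the content of the final adverse-event tables or the efficacy analysis.

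**Working it through.** No arithmetic applies: the plan gives one figure, 48 hours, and it is the same in both places. The check is a comparison of text.

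| Section | Events covered | Requirement | Time limit to sponsor |
|---|---|---|---|
| B.6.21 | SAEs, no causality qualifier | Failure to report is a possible reason for action against a site | 48 hours |
| E.3 | SAEs that are study-related | Investigator must report | 48 hours |
| B.8.3.1 | Relationship: every AE. Seriousness: listed for study-related AEs | Investigator assessment | None |
| B.8.3.2 | Source worksheet: all AEs and SAEs. EDC: events judged unrelated are left out | Capture at site, IRB reporting as required | None |

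Now follow one serious event that the investigator judges unrelated.

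1. **Relatedness.** The investigator decides it (B.8.3.1, E.3), knowing the assignment (B.5.4).
2. **Seriousness.** B.8.3.1 lists this assessment only for study-related events, so read literally the event need not be classed as serious at all. That does not fit with E.3, which makes the investigator responsible for seriousness generally. Nor does it fit with B.8.3.2, whose worksheet rule presupposes that SAEs have been identified, or with the B.8.3.1 rule that back or leg pain need be reported only if it meets the SAE definition, which requires seriousness to be judged first.
3. **Database.** B.8.3.2 leaves the event out of the EDC.
4. **48-hour duty.** E.3 does not reach it. B.6.21 would, but only if a list of reasons for action against a site is read as creating a reporting duty.
5. **Other routes.** Three remain:
   - source documents reviewed at periodic monitoring visits (E.1.2), whose frequency is left to a separate monitoring plan;
   - reporting to the IRB under its own rules (B.8.3.2), which goes to the IRB and not to the sponsor;
   - a Study Termination eCRF giving the reason, if the subject withdraws early (B.6.19).

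   None states a 48-hour limit for the sponsor.

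The plan therefore sets no time limit for this event to reach the sponsor, unless the B.6.21 item is taken to set one.

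**The case against.** The strongest reply is that B.6.21 creates no competing duty. Its list is of possible reasons and is discretionary. The item repeats the 48 hours, the trigger of knowledge of the event and the IRB clause found in E.3, so it may simply be shorthand for a breach of E.3. This is a fair reading, though nothing in the text says so. A reader might infer that a site could be suspended for doing exactly what E.3 asks. The documents do not support that: the item is discretionary and can be read in line with E.3.

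Second, the study-related scope looks deliberate. B.8.3.1, B.8.3.2, E.1.2 and E.3 all use it, in a post-market study of an approved device. Adding the qualifier to B.6.21 would remove the contradiction. That is true, but it would leave the lack of a deadline in place and make it explicit.

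Third, a reader might infer that sponsor review is the only safety check across sites. This is too strong. The IRB receives events as it requires and may suspend or terminate the study (B.6.21), monitors use source documents (E.1.2), and the sponsor may access medical records (E.2). E.3 and E.7 also cite federal regulations, and E.3 the sponsor's own procedures, but their content is not in the documents and cannot be assumed either to close the gap or to leave it open. What stands is that none of the routes described in the plan gives the sponsor a deadline for an SAE judged unrelated.

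**Conclusion.** The point holds as an inconsistency of scope between current sections, with a practical consequence: an unblinded investigator's causality opinion decides whether the sponsor is told of a serious event within 48 hours or at some unstated later time. The consequence is delay, not certain loss, because slower routes exist.

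A reader might want a count of SAEs falling outside the duty. The plan does not support one. It gives neither an expected SAE rate nor the share likely to be judged unrelated, so any count would only restate assumed rates. The single SAE in the feasibility study, in which 20 subjects completed, says nothing about how sites would classify events here.

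The conclusion rests on reading E.3 and B.8.3.2 as written and on no undisclosed procedure setting a deadline. It does not touch the primary endpoint, the margin or the power. The change should be made because it is cheap and improves safety oversight in a trial without a Data Monitoring Committee.

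**What to change.** Reconcile the four sections to one scope.

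- **E.3 and B.6.21:** both to cover every SAE, reported to the sponsor within the existing 48 hours of knowledge regardless of relatedness. The investigator's causality opinion is attached, and the sponsor records its own.
- **B.8.3.1:** seriousness to be assessed for every adverse event, not only those judged study-related.
- **B.8.3.2:** SAEs to be excepted from the rule that keeps events judged unrelated out of the EDC.

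Changing E.3 alone would not be enough, because B.8.3.1 and B.8.3.2 would still let an unrelated serious event go ungraded and unentered. The cost is conforming edits in four sections and a few extra SAE forms. Capture on the site worksheet and the 48-hour process already exist, and non-serious events judged unrelated can stay outside the EDC as now.
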